NCT#: NCT03587974

Document Date: April 2, 2018

Document Type: Study Protocol

1) Protocol Title

Title: Randomized controlled trial to test the feasibility, acceptability and preliminary effectiveness of a psychosocial intervention to support Alzheimer's family caregivers in Vietnam

Protocol Version Date: 4/2/2018

2) Objectives

The objective of this study is to conduct a randomized controlled trial to test the preliminary effectiveness, feasibility and acceptability of a psychosocial intervention to support Alzheimer's family caregivers in Vietnam. In terms of preliminary effectiveness, our hypothesis is that caregivers in the intervention will show lower psychological distress and lower caregiver burden compared with those in the control group.

3) Background

Low and middle-income countries (LMIC) such as Vietnam are undergoing a dramatic demographic transition that will result in a substantial increase in the number of older adults, including those afflicted with Alzheimer's disease and related dementias, over the next several decades. Dementia is among the most disabling and costly neurodegenerative brain diseases. Strengthening LMIC capacity to support family caregivers of persons with dementia through low-cost and sustainable non-pharmacological approaches, such as education and skill-building to deal with difficult behaviors, is vital to avoid costly and ineffective alternatives such as psychotropic medications or institutionalization, and to reduce caregiver burdens and depression. While evidence-based non-pharmacological treatments exist in high income countries (HIC), these interventions have not been adapted for use in Vietnam and other LMIC.

This project addresses these gaps by testing a community-based and culturally adapted behavioral family caregiver intervention for use in Vietnam. The intervention has several components (psychoeducation, stress reduction, skill-building) and is designed to reduce caregiver stress and burden. This project also builds directly on two preliminary studies, including interviews with key stakeholder and a case series. These preliminary studies demonstrated the acceptability of the intervention model but also identified areas for modification to tailor the intervention to the social, economic, and cultural circumstances in Vietnam.

4) Inclusion and Exclusion Criteria

Alzheimer's family caregivers will be identified through a registry of persons with dementia at the Vietnam National Geriatric Hospital in Hanoi.

Page 1 of 8 Revised: February 27, 2017

To be eligible, the person will be an adult who is the identified primary adult caregiver (i.e. the person spending the most time day-to-day providing care) to an older adult who is living in the community and has received a diagnosis of Alzheimer's disease or another degenerative dementia. All participants will be living in the Soc Son area outside Hanoi, Vietnam.

The final sample will be 50 family caregivers of persons diagnosed with dementia (25 in the active intervention and 25 in the control group). The study will exclude

- Adults unable to consent
- Individuals who are not yet adults (infants, children, teenagers)
- Prisoners
- Pregnant women.

5) Study Timelines

- Each family caregiver will participate in the study for 3 months.
- We will enroll subjects from April 1 through the end of September, 2018.
- We will complete preliminary analysis of the data by the end of January of 2019.

6) Study Endpoints

This is a time-limited intervention lasting up to 3 months.

7) Procedures Involved

This is cluster randomized controlled trial to pilot-test a culturally adapted behavioral intervention to support Alzheimer's family caregivers.

Participants in the intervention clusters will receive a manualized intervention that will consist of 3-6 one-hour sessions with a trained health professional (e.g. nurse, social worker, or physician) who has been certified to deliver the intervention. The sessions will be administered in the home (or other setting of the subject's choice such as a clinic) and include several components, including psychoeducation, stress reduction, skill-building. The intervention will be tailored to the needs and preferences of the caregiver.

Participants in the control clusters will receive education about Alzheimer's disease including written informational materials at the time of enrollment (i.e., 1 session).

Participants in both clusters will also be assessed at baseline and at the end of the intervention. These assessments will occur at baselineand 3 months to and will assess primary and secondary outcomes using standardized instruments (i.e., items embedded in Risk Priority Intake Assessment).

A research protocol will be used that includes scripts, study scales detailed descriptions of the goals for each session, and standardized forms (see attached study manual).

Page 2 of 8 Revised: February 27, 2017

8) Data and/or Specimen Management and Confidentiality

The primary study outcomes are burden of caregiving (Zarit Burden Inventory) and caregiver distress (PHQ-4), found on pages (RP)4 and (RP)5 of the REACH Interventionist Notebook respectively. Secondary outcomes include Alzheimer's disease knowledge (Alzheimer's knowledge scale)

Procedures for maintenance and confidentiality include 1) assigning each participant a unique identifier, 2) data collected will be labeled using the unique identifier and will be stored separately from the key linking personal information (e.g. name, date of birth, address, phone number) and identifiers, 3) all data will be kept under lock and key or on a secure server that is only accessible to research staff, 4) at the conclusion of the study, the key linking identifiers and personal information will be destroyed, 5) all research personnel in the US who have access to the patient data will receive training on conducting human research (e.g. NIH online course) – all investigators in Vietnam will participate in the local equivalent of this training.

9) Data and/or Specimen Banking

All data will be stored on a secure server at in Vietnam. De-identified data will be transferred to UC Davis and the University of South Carolina electronically through an encrypted zip file. After the study, the key linking personal identifiers to the survey data will be destroyed.

10) Provisions to Monitor the Data to Ensure the Safety of Subjects

The goal of this randomized controlled trial care is to assess feasibility, acceptability, and preliminary effectiveness of the behavioral intervention to support Alzheimer's family caregivers. Case review will occur on a weekly basis with a team that includes the care manager and the local PI and one investigators from the UC Davis and the U of SC. The caregiver's level of distress and any indicators of elder abuse/neglect will be reviewed at each session.

This study will have a Safety Officer (SO) but will not have a DSMB. The rationale for not having a DSMB is that this is a single-site, minimal risk clinical trial with a relatively small number of subjects at a single site. The lead investigators (i.e. Co-PIs [name] and [name] as well as the lead investigator at the National Geriatric Hospital, [name]) will meet quarterly with Safety Officer during the clinical trial. During these meetings, the SO responsibility will be to review the progress of the study, adverse events, procedures for maintaining the confidentiality of data, and the quality of data collection, management, and analyses. The SO will also review any issues that arise in terms of conflict of interest. The SO will be a senior neurology faculty from the National Geriatric Hospital who is not directly involved in the study.

Page 3 of 8 Revised: February 27, 2017

For this study, [name] will have primary responsibility for coordinating the collection, review and reporting of adverse events. Adverse events (AE) including serious adverse events (SAE) will be collected and reported to the IRBs at all three collaborating institutions on a regular basis. At the monthly meetings of the research team, all incident adverse events will be graded in terms of their seriousness and their likely relationship to the psychosocial intervention. All serious adverse events determined to have a likely relationship to the psychosocial intervention will be reported to the SO for this study, to the IRBs for each institution, and to NIA by the next business day (e.g. usually within 24 hours). Consistent with NIA guidelines, we will define serious adverse events as those that results in death, are life threatening, or places the participant at immediate risk of death from the event as it occurred, requires or prolongs hospitalization, causes persistent or significant disability or incapacity, is another condition which investigators judge to represent significant hazards.

Cases of potential elder abuse/neglect and caregiver suicidal ideation will be handled according to study protocols that are consistent with local practice in Vietnam. Field staff will report all suspected cases of elder abuse/neglect within 24 hours to study investigators [name] (neurologist) and [name] (a geriatrician) at the National Geriatric Hospital. After consultation with the research team including Drs. [name] (a geriatric psychiatrist) and [name] (a social worker), [name] may take additional steps, including contacting and directly assessing the situation, educating family members about abuse, and referring families to local services (e.g. temples, elder clubs, social work services) for counseling and support. Similarly, field staff will report to [name] any caregivers who express suicidal ideation. [name] will then directly contact and assess the caregiver and determine if additional steps are necessary, including referring the caregiver for counseling, support and/or hospital-based mental health and social services. Field staff, usually nurses or social workers, will be trained in these written protocols by the study staff (i.e. [name] and [name]). All cases of elder abuse and caregiver suicidal ideation will be treated as adverse events and discussed at monthly research meetings and reported to each institution's IRB. [name] will report serious adverse events to the SO and NIA.

11) Withdrawal of Subjects

Subjects (patients and family members) may withdraw at any time. If they withdraw from the study, they will be given the option of having their records destroyed.

Page 4 of 8 Revised: February 27, 2017

12) Risks to Subjects

There are two main risks associated with this study: 1) discomfort or mild distress because of the intervention and 2) inconvenience because of the need to fill out the study questionnaires. These risks are similar to the risk of undergoing routine assessments in healthcare clinics in Vietnam. Specific steps are being taken to address each category of risk.

Discomfort due to the intervention: Even though this study builds on evidence-based strategies for support of family caregivers, subjects may experience discomfort or mild distress when discussing their caregiving experience or because of concerns about confidentiality. These risks are being minimized in several ways. First, caregiver will be given the option of discussing issues privately with the care manager during the intervention. Second, the care manager will be trained to monitor the nature of interactions between patients and family members and any serious issues that emerge will be discussed with the supervising team so that strategies can be developed to address any issues that arise. Finally, subjects will have the opportunity to drop out of the family-centered arm of the study and complete treatment by themselves or drop out of the study altogether.

Inconvenience due to questionnaires: To address the inconvenience associate with completing study questionnaires, we will give subjects the option of completing these in the home or by phone. In addition, during the consent process, participants will be advised that they can choose not to answer any questions that make them feel uncomfortable. Risks to subjects are minimal for several reasons.

This is a behavioral intervention and does not involve drug treatment. In prior studies conducted in the US with multi-cultural populations in the United States there have not been any serious adverse side events attributable to the intervention (personal communication with one of the PIs of a large-scale national study). It is also possible that elder/abuse or neglect may be detected during the study and require intervention. A protocol for handling cases of abuse/neglect according to local norms/resources has been developed in collaboration with our colleagues in Vietnam.

13) Potential Benefits to Subjects

There are several potential direct benefits to subjects. Subject may experience an increase in their knowledge and skills because of the intervention. In addition, caregivers will learn stress reduction techniques that may help reduce caregiving-related distress.

Participants will receive \$10 at the end of each study visit (including both intervention sessions and visits for administration of questionnaires).

Page 5 of 8 Revised: February 27, 2017

14) Multi-Site Research

This is a single-site, multiple PI, international study and [name] is the lead investigator. [name] will be responsible for ensuring that all sites have the most current version of the protocol and consent document. He will also be responsible for ensuring that 1) All required approvals have been obtained at each site (including approval by the site's IRB of record), 2) All modifications have been communicated to sites, and approved (including approval by the site's IRB of record) before the modification is implemented, 3) All engaged participating sites will safeguard data as required by local information security policies, 4) All local site investigators conduct the study appropriately, and 5) All non-compliance with the study protocol or applicable requirements will reported in accordance with local policy.

15) Community-Based Participatory Research

NA

16) Provisions to Protect the Privacy Interests of Subjects

Describe the steps that will be taken to protect subjects' privacy interests. "Privacy interest" refers to a person's desire to place limits on whom they interact or whom they provide personal information.

Describe what steps you will take to make the subjects feel at ease with the research situation in terms of the questions being asked and the procedures being performed. "At ease" does not refer to physical discomfort, but the sense of intrusiveness a subject might experience in response to questions, examinations, and procedures.

Indicate how the research team is permitted to access any sources of information about the subjects.

17) Compensation for Research-Related Injury

NA – minimal risk study

18) Economic Burden to Subjects

There are no costs that subjects may be responsible for because of participation in the research.

19) Drugs or Devices

NA

Page 6 of 8 Revised: February 27, 2017

20) ClinicalTrials.gov Registration

Section 1: NIH Funded Studies

If yes to BOTH, the study must be registered on Clinicaltrials.gov.

Yes	
	This study is funded by the NIH. (If this study is not funded by NIH, go to Section
	2.)
	One or more human subjects will be prospectively assigned to one or more
	interventions (which may include placebo or other control) to evaluate the effects of
	those interventions on health-related biomedical or behavioral outcomes.

Section 2: Studies subject to FDA jurisdiction

If yes to ANY the study must be registered on Clinicaltrials.gov.

Yes	
	This is a prospective clinical study of health outcomes in human subjects that compares an intervention with an FDA-regulated device against a control. This is not a small clinical trial to determine the feasibility of a device, or a clinical trial to test prototype devices where the primary outcome measure relates to feasibility and not to health outcomes.
	This is a pediatric postmarket surveillance of a device as required under section 522 of the Federal Food, Drug, and Cosmetic Act.
	This is a controlled clinical investigation, other than a phase I clinical investigation, of a drug subject to section 505 of the Federal Food, Drug, and Cosmetic Act or to section 351 of the Public Health Service Act.

To view a flowchart describing applicable clinical trials subject to FDA jurisdiction click here.

Section 3: Publishing the results

If yes to BOTH the study must be registered on Clinicaltrials.gov.

Yes	
	This study prospectively assigns people or a group of people to an intervention, with
	or without concurrent comparison or control groups, to study the cause-and-effect
	relationship between a health-related intervention and a health outcome.
	The PI has access to and control over all the data from the clinical trial and has the
	right to publish the results of the trial and plans to publish the results in a journal
	that follows the ICMJE recommendations.

This requirement includes studies of behavioral interventions.

Section 4: Registration on Clinicaltrials.gov is not required

Yes	
	I have read sections 1-3 above and registration on clinicaltrials.gov is not required for this research.

Page 7 of 8 Revised: February 27, 2017

21) Criteria for 10 Year Approval

If yes to all items below this research may qualify for a 10-year approval period.

Yes	
\boxtimes	This research involves no more than minimal risk.
	This research does not receive any federal or state government funding or funding
	from a private funder who requires annual review per contract.
	This research is not subject to FDA jurisdiction.
	This research does not include prisoners as participants.
	This research is not subject to SCRO oversight.
	This research is not subject to oversight by the Research Advisory Panel of
	California (RAP of C).
	This research does not involve identifiable information held by the State of
	California Department or Agency
	No personnel involved in the design, conduct, or reporting of this research have a
	new unreported related financial interest (RFI) in this study.

Page 8 of 8 Revised: February 27, 2017

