Study Title: Randomized controlled trial to test the feasibility, acceptability, and preliminary effectiveness of a psychosocial intervention to support Alzheimer's family caregivers in Vietnam.

NCT#: NCT03587974

Document Date: March 1, 2020

Document Type: Statistical Analysis Plan

Statistical Analysis Plan

Characteristics of the caregivers and the care recipients will be compared between the two groups using a two-sample t-test or Chi-square test; the Wilcoxon rank sum test or Fisher's exact test will be used if needed due to violations of the underlying assumptions. Primary analysis of the intervention effect will use an intent-to-treat approach, in which groups were compared based on randomization assignment. To account for the clustering of participants by commune, mixed effects models that included a cluster-specific random effect will be used to estimate differences between groups. Models will utilize the post-intervention assessment as the outcome and included the baseline assessment as a covariate. The post-intervention assessment will be divided by the standard deviation in the entire sample at baseline, so that interpretation of model coefficients will be in terms of standard deviation units. Model assumptions will be checked and met by the data. All analyses will be conducted in SAS, version 9.4, and a *p*-value less than 0.05 considered statistically significant.

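### Does the plan need a rule on who collects the 3-month Zarit and PHQ-4, and in what mode?

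*Protocol*

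**What the plan says.** Section 7 of the protocol sets the timing: "Participants in both clusters will also be assessed at baseline and at the end of the intervention", that is, at baseline and 3 months. It names no assessor. It then refers to working documents that include scripts, scales and "standardized forms (see attached study manual").

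Section 8 names the Zarit and the PHQ-4 as primary outcomes and says they are "found on pages (RP)4 and (RP)5 of the REACH Interventionist Notebook".

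Section 12 lists as a risk "inconvenience because of the need to fill out the study questionnaires" and, to ease it, offers the "option of completing these in the home or by phone". Section 13 pays caregivers for each visit, "including both intervention sessions and visits for administration of questionnaires".

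Section 10 gives the Safety Officer, at quarterly meetings, review of "the quality of data collection, management, and analyses".

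The SAP's primary analysis is a mixed model with a random effect for commune: "Models will utilize the post-intervention assessment as the outcome and included the baseline assessment as a covariate". It has no term for assessor or mode.

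**The concern.** The two arms differ greatly in staff contact: 3-6 one-hour sessions in intervention clusters against one education session in control clusters. Both primary outcomes are what the caregiver chooses to report. If the person who delivered the sessions also asks the questions at 3 months, courtesy could lower reported burden and distress. Rapport could instead raise disclosure and push scores the other way. Either effect would probably differ by arm. It would arise only after baseline, so the baseline covariate cannot absorb it, and intent-to-treat does not address it.

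Two details make collection by treating staff plausible. The primary scales sit in a notebook written for interventionists, and section 10 has the caregiver's distress reviewed at each session, which touches the same construct as one primary outcome. The home-or-phone option adds a second unknown, because nothing requires the 3-month mode to follow the baseline mode or to be recorded. At stake is whether a difference significant at 0.05 could partly reflect the interviewer, and whether a reader could tell.

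**Working it through.** **Is there a rule anywhere?** The relevant text, side by side:

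| Place | What it settles | What it leaves open |
|---|---|---|
| Protocol section 7, assessments | Both arms, baseline and 3 months | The assessor |
| Protocol section 7, study manual | Scripts and forms exist | Their content; the manual was not supplied |
| Protocol section 8, notebook | Where the scales are printed | Who administers them |
| Protocol section 12, filling out forms | Suggests self-completion | Does not exclude an interviewer |
| Protocol section 12, home or phone | Mode is the caregiver's choice | A phone call normally means some interviewing |
| Protocol section 13, payment | Questionnaire visits are listed apart from sessions | Whether different staff run them |
| SAP | Adjusts for baseline score and commune | Assessor and mode |

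No supplied text names the collector or requires matching modes. Equally, none says that treating staff collect outcomes. The wording in sections 12 and 13 points, without proving it, towards self-completed forms at separate visits.

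**How large could an effect be?** The plan gives no figure to reproduce: there is no effect size, ICC, number of communes or estimate of reporting shift. What follows is illustration only.

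From the documents: 50 caregivers, 25 per arm; significance level 0.05 (taken as two-sided, since the SAP does not say); baseline covariate; commune random effect.

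Assumed: k = 6, 8, 10 or 12 communes; ICC 0.01, 0.05 or 0.10; baseline-outcome correlation 0.5; t reference with k-2 degrees of freedom.

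Standard error in SD units:

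SE = sqrt[(1 - 0.5²) × (4/50) × (1 + (50/k - 1) × ICC)]

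- Smallest (k = 12, ICC 0.01): sqrt(0.75 × 0.08 × 1.0317) = 0.249
- Largest (k = 6, ICC 0.10): sqrt(0.75 × 0.08 × 1.7333) = 0.322

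Chance of a false benefit on one outcome with no true effect = P[noncentral t (k-2 df, ncp = shift/SE) > t(0.975, k-2)]. With no shift it is 2.5%. If a fraction of the intervention scores shifts, the net shift is that fraction of the full one.

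| Shift per affected score | All intervention scores affected, no control scores | Half the intervention scores affected, no control scores |
|---|---|---|
| 0.10 SD | 4.3-5.5% | 3.3-3.8% |
| 0.20 SD | 7.1-10.9% | 4.3-5.5% |
| 0.30 SD | 10.9-19.3% | 5.6-7.9% |

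If the shift runs against the intervention and the true benefit is 0.5 SD, the ncp is (0.5 - shift)/SE. Power falls from 22-44% with no shift to 16-31%, 11-19% and 7-11% for shifts of 0.10, 0.20 and 0.30 SD.

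A normal reference with both tails, correlation 0 to 0.7 and design effect 1.0 to 1.2 gives higher figures: about 6-8%, 10-17% and 16-32% for the three shifts in all intervention scores. The direction is the same; the level depends on the assumptions.

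**Does mode matter separately?** A change from home to phone biases the arm contrast only if it happens more in one arm or acts differently by arm. The documents give no reason to expect either. The distinction that bears on interviewer influence is self-completed against interviewer-administered, and a home visit could be either. A home-or-phone rule would therefore not settle the question it is meant to answer.

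**The case for a change.** The case for a change is respectable. The omission is certain in the supplied text. Preliminary effectiveness is a stated objective and is tested at 0.05, so interviewer influence bears on a result that will be reported. Unequal contact makes a differential effect credible, and the SAP model cannot correct it. The change would be cheap: two sentences in section 7, two form fields and one table by arm, all scores kept in the intent-to-treat analysis, with the table going to a Safety Officer who already reviews the quality of data collection.

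The mechanism stands, and so does the point that a reader of the protocol and SAP cannot judge it. What does not follow is that the plan needs changing. The rule may already be in the manual. The documents give no staff numbers, and sections 10 and 12 speak of a single care manager, so a separate assessor may not be available. A rule limited to what staffing allows would guarantee only a record. Mode matching would narrow the choice that section 12 offers to reduce inconvenience, and could cost 3-month data in a trial of 50. Nor would a separate assessor remove the reporting bias of caregivers who know what they received, so the share of any bias due to the collector's identity is unknown.

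**Conclusion.** No change to the plan follows. The protocol and SAP do not name the 3-month collector, but this is missing operational detail, not a stated rule that is wrong. The study manual is its natural home, and a trial team would ordinarily settle it there. The wording on filling out forms and on separate questionnaire visits makes collection by treating staff the less likely reading, though it does not exclude it.

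The possible effect is not trivial in the worst case: up to 19.3% false benefit at 0.30 SD under the main set of assumptions. That case needs every intervention score and no control score to shift in one direction. With half the intervention scores affected, the same shift gives 5.6-7.9%. The shift, its sign, the number of communes, the ICC and the correlation are all assumed. The concern over mode has no arm-specific argument behind it.

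This conclusion rests on the manual being silent or sensible. If it assigned the 3-month interviews to the professional who ran the sessions, that would belong among the limitations when results are reported. Optionally, the report could say who collected the scales and whether forms were self-completed or interviewer-administered, by arm. The planned analysis would be the same either way.

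### Do two unranked primary outcomes, with no rule for a split result, leave the pilot's effectiveness hypothesis open?

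*Protocol*

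**What the plan says.** The primary outcomes appear in protocol section 8 (Data and/or Specimen Management and Confidentiality): "The primary study outcomes are burden of caregiving (Zarit Burden Inventory) and caregiver distress (PHQ-4"). They are not ordered or weighted. Alzheimer's knowledge is listed separately as secondary. Section 6 (Study Endpoints) names no endpoint; its only content is "This is a time-limited intervention lasting up to 3 months".

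Section 2 (Objectives) states the effectiveness hypothesis, which it labels preliminary: "our hypothesis is that caregivers in the intervention will show lower psychological distress and lower caregiver burden compared with those in the control group". Section 7 describes the study as a "cluster randomized controlled trial to pilot-test a culturally adapted behavioral intervention", and section 4 fixes the size: "The final sample will be 50 family caregivers of persons diagnosed with dementia (25 in the active intervention and 25 in the control group").

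The SAP is one paragraph. It fits mixed models with a commune random effect and baseline adjustment, scaled to baseline SD units. On the outcome it says only "Models will utilize the post-intervention assessment as the outcome", and it applies one threshold, p "less than 0.05 considered statistically significant". It does not state sidedness, an order of testing, a co-primary rule or a multiplicity adjustment.

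**The concern.** Two primary outcomes, each tested at 0.05, raise the question of what counts as support for the hypothesis. If either is enough, the chance of a false claim of benefit is larger than for one test. If both are needed, power falls. The documents do not choose. The hypothesis uses 'and', which leans towards requiring both, but a hypothesis is not a decision rule.

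What is at stake is the split result. Under the plan as written, the same split could be described afterwards as supporting the hypothesis or as failing it. In a trial this small a split is plausible, so the gap is not merely theoretical.

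**Working it through.** **Inputs from the documents.** Two primary outcomes (protocol section 8); 25 caregivers per arm (section 4); threshold 0.05 (SAP). The documents give no effect size, power, intracluster correlation, number of communes or correlation between outcomes, so the sample size of 50 cannot be reproduced and there is no stated family-wise error rate to check.

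**Assumptions.** Two-sided tests; correlation between the two test statistics r = 0.3, 0.5, 0.7; each test holds its own level; 47 degrees of freedom (50 minus intercept, arm and baseline covariate); no clustering and no gain from the baseline covariate unless stated.

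**Step 1. False claim of benefit when neither outcome has a true effect.** Each test errs in the benefit direction with probability 0.025. P(both) is the bivariate normal probability that both statistics exceed 1.96, and P(either) = 0.025 + 0.025 − P(both).

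| r | both required | either enough |
|---|---|---|
| 0.3 | 0.0024 | 0.0476 |
| 0.5 | 0.0046 | 0.0454 |
| 0.7 | 0.0083 | 0.0417 |

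The reference for one test is 0.025. If one outcome has a true effect and the other has none, the both-required rate can approach 0.025 but not exceed it. Requiring both therefore causes no inflation. Only an either-is-enough rule does, and neither document states one.

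**Step 2. Power per outcome.** The noncentrality is d × √(25/2) = 3.536 × d, and the critical value is t(0.975, 47) = 2.012.

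- d = 0.8: noncentrality 2.828, power 0.791
- d = 0.5: noncentrality 1.768, power 0.410
- d = 0.4: noncentrality 1.414, power 0.283
- d = 0.2: noncentrality 0.707, power 0.103

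**Step 3. Split results.** With powers p1 and p2, P(both) = Φ2(Φ⁻¹(p1), Φ⁻¹(p2); r), where Φ2 is the bivariate normal distribution function, and P(split) = p1 + p2 − 2 × P(both). For 0.8 SD on both at r = 0.5, this is 2 × 0.791 − 2 × 0.675 = 0.232.

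| true effects (SD) | P(both), r = 0.3 / 0.5 / 0.7 | P(split), r = 0.3 / 0.5 / 0.7 |
|---|---|---|
| 0.5 and 0.5 | 0.214 / 0.248 / 0.287 | 0.391 / 0.324 / 0.246 |
| 0.8 and 0.8 | 0.653 / 0.675 / 0.702 | 0.276 / 0.232 / 0.179 |
| 0.8 and 0.4 | 0.251 / 0.266 / 0.278 | 0.572 / 0.541 / 0.518 |
| 0.8 and 0.2 | 0.094 / 0.100 / 0.102 | 0.706 / 0.695 / 0.689 |
| 0.2 and 0.2 | 0.023 / 0.034 / 0.048 | 0.160 / 0.138 / 0.109 |

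The split probability thus runs from about 11% to 71%, depending on effects that the documents do not give. It is a minority result only when the true effects are similar.

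**Step 4. Clustering.** With an assumed design effect of 1.5 and baseline correlation of 0.5, the noncentrality is multiplied by 1/√(1.5 × 0.75) = 0.943. At 0.8 SD on both, power per outcome falls to 0.743 and the split is 0.315 / 0.264 / 0.202. This still uses 47 degrees of freedom, which is optimistic for a trial randomised by commune. The powers in step 2 are likewise optimistic about clustering.

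**Step 5. What the choice of rule does.** At 0.8 SD and r = 0.5, the chance of declaring support is 0.675 if both are required and 2 × 0.791 − 0.675 = 0.907 if either is enough.

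**The case for a change.** The strongest case for a change is that step 5 shows a real difference between the two rules, that splits are common in a trial this small, and that the SAP is where a hypothesis becomes an analysis. One sentence would settle the reading, at no cost in data.

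The facts behind this stand: neither document contains the sentence, and a split could be described in two ways. Three things limit what follows.

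- The identity of the outcomes is not in doubt. The protocol names both primaries and separates the secondary, and the SAP's baseline and post-intervention assessments map onto the two assessments in protocol section 7. Placing the outcomes in section 8 rather than section 6 is an editorial matter.
- The sentence would impose a binary verdict on a pilot whose SAP estimates group differences in SD units. Reporting two estimates, each with its own p-value, is a sound pilot output. Statisticians could reasonably disagree about going further, and requiring both costs 9 to 14 percentage points of power at 0.8 SD (79% against 70% to 65%).
- The timing weakens the gain. Protocol section 5 says "We will complete preliminary analysis of the data by the end of January of 2019", and the SAP is dated March 1, 2020. If the protocol's schedule was kept, a rule added now would not be prespecified and would give little protection against a reading chosen after the result.

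**Conclusion.** No change to the plan follows. This is a missing detail that analysts would fill sensibly, and adding a rule would be a trade-off rather than a correction. No stated error rate is wrong. Under the reading that the hypothesis favours, 0.05 per outcome needs no adjustment: with no true effect on either outcome, a false claim that both improved has probability 0.2-0.8% for r between 0.3 and 0.7. The rise to 4.2-4.8%, against 2.5% for one test, needs an either-is-enough rule that the documents do not contain.

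A split is likely enough to be worth noting: 18-39% with equal effects of 0.5 or 0.8 SD, and 52-71% with the unequal effects shown. These figures rest on assumed effects, correlations and two-sided tests, and they ignore commune clustering. In a split, the plan still leads to the right conclusion outcome by outcome, with an estimate and a test for burden and another for distress. For preliminary effectiveness that is sufficient, provided both outcomes are reported, as their joint status as primary outcomes already implies.
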